cohort and any cumulative safety data of all cohorts as the trial advances to determine the acceptability to escalate to the next mRNA-1893 dose level. The 30 participants in the first cohort will continue to receive their second study vaccine dose on Day 29 (+14 days).

The blinded IST will oversee the safety of the trial and will review safety data to ensure adherence to the protocol, will monitor safety laboratory test results and reactogenicity, and may request input from the SMC should the study meet pause rules or for any other study events that could potentially affect participant safety. The IST will approve escalation to the next higher dosing cohort after review of blinded safety data of the currently dosed cohort through 7 days after the first vaccination and any cumulative safety data of all cohorts as the trial advances.

A diagram of the dosing schema by cohort is shown in Figure 1.

[figure not shown]

Figure 1: Dosing Schema by Cohort

Abbreviations: IST = internal safety team; S- = flavivirus seronegative; S+ = flavivirus seropositive.

Note: For each dose cohort (Cohorts 1 through 4), Safety Oversight will be performed 7 days after the first 5 participants (all flavivirus-seronegative) are randomly assigned and receive their first study vaccination (Day 1) before randomly assigning the remaining 25 participants in the cohort. Seven days after all 30 participants in the cohort have received the first study vaccination and review of all available safety data has been performed (ie, no safety concerns and pause rules have not been met), the IST will determine the acceptability to escalate to the next mRNA-1893 dose level.

During the Vaccination Phase, participants will be instructed to contact the Investigator immediately should they develop any untoward signs or symptoms or any medical occurrence that leads to an unplanned visit to a health care practitioner, hospitalization, or an emergency room visit. In case of MAAEs, if the participant presents with clinical symptoms

that may suggest a dengue infection, a blood sample should be collected for testing of dengue infection. In addition, participants will be instructed to contact the site within 24 hours, in the event of any severe Grade 3 local and systemic reactogenicity AE (solicited AEs; Section 3.5.6) or any episode of rash within 6 days after study vaccination.

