6	Any ≥ Grade 3 unsolicited adverse event in an mRNA-1893 cohort ^b that cannot be reasonably attributed to a cause other than vaccination OR Any ≥ Grade 3 laboratory abnormality ^c in an mRNA-1893 cohort ^b that cannot reasonably be attributed to a cause other than vaccination	≥ 20% and ≥ 2 participants/group	

^a For the first 5 participants in each dose level cohort, the pause rule will be considered met if 2 of the first 5 participants experience the same event regardless of dosing group.

If a pause is triggered in the study, each participant's clinic visits will continue until the next scheduled vaccination visit. If a pause affects a participant's vaccination visit, the window for that participant's vaccination visit will be suspended until the pause is lifted and vaccination can resume. Once the pause is lifted at a site, vaccination should be reinstated as soon as possible. Clinic visits should thereafter (Day 36 [+3 days], Day 57 [-7/+14 days], Month 7 [± 14 days], and Month 13 [± 14 days]) be scheduled as if participants had received their second vaccination within the 28 (+14) day window. The Dose 2 window may be extended to 28 (+14) days at the discretion of the principal investigator and with approval of the study medical monitor on a case by case basis for participants whose window is affected by a study pause.

b The rate of adverse events and laboratory abnormalities will be computed based on the number of exposed participants who have provided safety data (i.e., have completed a post-dosing visit for assessment of safety).

Grading of laboratory parameters will be based on the US Food and Drug Administration Guidance for Industry "Toxicity grading scale for healthy adult and adolescent volunteers enrolled in preventive vaccine clinical trials" (DHHS 2007).

If a pause is prolonged such that the second vaccination takes place outside the 28 (+14) day window, the Sponsor has the option to add additional participants in a dosing cohort to achieve the original number of participants planned for dosing within the 28 (+14) day window. If a participant is in the Screening Phase for more than 28 days as the result of a pause, the participant may be rescreened for study eligibility (and will receive a new screening number) as long as the participant continues to provide consent to participate in the study.

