3.5.7.2 Eliciting and Documenting Adverse Events

The investigator is responsible for ensuring that all AEs, SAEs and AESI are recorded in the eCRF and reported to the Sponsor. Unsolicited AEs will be assessed during the Vaccination Phase from the time of the first dose administration at Day 1 through Day 57 (±7 days). Serious AEs, MAAEs, and AESI will be assessed from Day 1 through Month 13 (EOS Visit), as specified in the Schedule of Events (Table 5). Any AEs occurring before receipt of the vaccine will be analyzed separately from TEAEs.

At every clinic visit or telephone contact, participants will be asked a standard question to elicit any medically-related changes in their well-being according to the scripts provided. Participants will also be asked if they have been hospitalized, had any accidents, used any new medications, or changed concomitant medication regimens (both prescription and over-the-counter medications).

In addition to participant observations, data from clinical laboratory test results, physical examination findings, or other documents relevant to participant safety classified as an AE will be documented on the AE page of the eCRF.

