| SAS | Statistical Analysis System | |
| SD | standard deviation | |
| SOC | system organ class | |
| TEAE | treatment-emergent adverse event | |
| ULOQ | upper limit of quantification | |
| ZIKV | Zika virus | |

Protocol mRNA-1893-P101

1 Administrative Structure

This study is being conducted under the sponsorship of ModernaTX, Inc. The safety and immunogenicity statistical analyses are being performed under contract with PPD in collaboration with ModernaTX, Inc.

2 Introduction

This statistical analysis plan (SAP), which describes the planned analyses for Study mRNA-1893-P101, is based on the most recent approved clinical study protocol, Version 2.0, dated 17 July 2019 and the most recent approved electronic case report form (eCRF) Version 5.0, dated 24 July 2019.

In addition to the information presented in the statistical analysis plans section of the protocol (Section 3.6) which provides the principal features of analyses for this study, this SAP provides statistical analysis details/data derivations. It also documents modifications or additions to the analysis plan that are not "principal" in nature and information that was not available at the time of protocol finalization.

PPD Biostatistics and Programming team, designee of Moderna Biostatistics and Programming department, will perform the statistical analysis of the safety, reactogenicity, and immunogenicity data; Statistical Analysis System (SAS; Version 9.4 or higher) will be used to generate all statistical outputs (tables, figures, listings, and datasets).

The SAP will be finalized and approved prior to the first interim analysis clinical database lock and treatment unblinding for the study. If the statistical analysis methods in this SAP differ from the methods described in the protocol, the SAP will prevail.

3 Study Objectives

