5.1 Overall Study Design

This is a Phase 1, randomized, observer-blind, placebo-controlled, dose-ranging study to evaluate the safety, tolerability, and immunogenicity of Zika vaccine mRNA-1893 administered to healthy flavivirus-seropositive and seronegative adult participants (18 to

Protocol mRNA-1893-P101

49 years of age, inclusive). A total of 120 participants (30 participants per cohort) will be enrolled into 1 of 4 mRNA-1893 dose cohorts (10, 30, 100, or 250 μg). Within each cohort, eligible participants will be randomly assigned to mRNA-1893 or placebo (4:1 mRNA-1893 to placebo) and administered the study vaccine as an intramuscular injection on a 2-dose vaccination schedule, 28 days apart (Day 1 and Day 29). Participants will be stratified by baseline flavivirus serostatus (seropositive and seronegative).

The study will comprise a Screening Phase (up to 28 days), a Vaccination Phase (up to 57 days), and a Long-Term Follow-up Phase (up to 12 months after last vaccination). Participants will have approximately 8 clinic visits with an additional 13 safety telephone calls. Study duration will be approximately 13 months for each participant. Participants will provide written informed consent before any study-specific procedures are performed.

Study vaccine dosing will begin with Cohort 1 (10 μ g mRNA-1893 or placebo), followed sequentially by Cohort 2 (30 μ g mRNA-1893 or placebo), Cohort 3 (100 μ g mRNA-1893 or placebo), and Cohort 4 (250 μ g mRNA-1893 or placebo).

For each dose cohort (Cohort 1 through 4), Safety Oversight will be performed 7 days after the first 5 participants (all seronegative) are randomly assigned and receive the first study vaccination (Day 1). Once safety is confirmed, the remaining 25 participants in the dose level cohort will be randomly assigned to dosing. Seven days after all 30 participants in the cohort have received the first study vaccination, a blinded internal safety team (IST) that is not directly involved in the day-to-day activities of the study, will review all available safety data for the currently dosed cohort and any cumulative safety data of all cohorts as the trial advances to determine the acceptability to escalate to the next mRNA-1893 dose level. The 30 participants in the first cohort will continue to receive their second study vaccine dose on Day 29 (+7 days).

[figure not shown]

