10.1 Appendix A Analysis Visit Windows for Safety and Immunogenicity Analysis

Table 3 Visit Window Mapping Rules

| Table 3 Visit Window Mapping Rules | | |
|---------------------------------------|--|----------------------------|
| Labs (Hem | atology, Chemistry, and Coagulation) and | l Vital Signs |
| Visit | Target Study Day | Visit Window |
| Day 1 | Date of First Vaccination (1) | Pre-dose |
| Day 1, 1 hour postdose – Vitals only | 1 | ≥ 1 hour post-dose |
| Day 8 - Labs only | 8 | [8,11] |
| Day 29 | Date of Second Vaccination (29) | [29,36] |
| Day 29, 1 hour postdose – Vitals only | 29 | ≥ 1 hour post-dose |
| Day 36 - Labs only | 36 | [36,39] |
| Day 57 (Month 2) – Labs only | 57 | [50,64] |
| | Adverse Events | |
| Stage | Vaccination | Target Time Frame |
| Vaccination | All | [1, 57] |
| Short-Term Follow-up | First | [1,29] |
| | Second | [29,57] |
| Long-Term Follow-up | First | NA |
| | Second | [57, Month 12 Safety Call] |
| Overall | All | [1, Month 12 Safety Call] |

Protocol mRNA-1893-P101

| Immunogenicity | | | | | |
|-------------------------------------|-------------------------------|------------|--|--|--|
| Visit Target Study Day Visit Window | | | | | |
| Day 1 | Date of First Vaccination (1) | Pre-dose | | | |
| Day 29 | 29 | [29,36] | | | |
| Day 57 (Month 2) | 57 | [50,64] | | | |
| Month 7 | 196 | [182,210] | | | |
| Month 13 | 364 | [343, 385] | | | |

Protocol mRNA-1893-P101

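### The SAP's Day 29 and Day 57 analysis windows are narrower than protocol V3.0 allows, and their fixed study days drop or mislabel laboratory results after a late second dose

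*SAP*

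**What the plan says.** Protocol V3.0 (17 March 2020) changed the Day 29 and Day 57 windows; its Summary of Changes gives COVID-19 as the reason. Section 3.1 now reads "The 30 participants in the first cohort will continue to receive their second study vaccine dose on Day 29 (+14 days"), and Section 3.4.2.2 lists "Day 57 [-7/+14 days], Month 7 [± 14 days], and Month 13 [± 14 days"]. Table 5 carries the same allowances.

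The SAP (v3.0, 25 May 2021) says in Section 2 that it "is based on the most recent approved clinical study protocol, Version 2.0, dated 17 July 2019". Section 5.1 reads "The 30 participants in the first cohort will continue to receive their second study vaccine dose on Day 29 (+7 days"). In Appendix A the immunogenicity windows are Days 29 to 36 for Day 29 and "Day 57 (Month 2) | 57 | [50,64"] for Day 57. The laboratory windows for those two visits are the same, with a further row "Day 36 - Labs only | 36 | [36,39"]. SAP 7.1 points to Appendix A for the windows of all study assessments. SAP 8 lists two departures from the protocol, and neither concerns windows. Section 2 also states: "If the statistical analysis methods in this SAP differ from the methods described in the protocol, the SAP will prevail".

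The per-protocol (PP) definition in SAP 6.2.2 requires samples inside acceptable windows but does not say which document defines them. SAP 7.1 defines two study-day counts, one from dose 1 and one from the most recent dose. Appendix A does not say which it uses.

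The protocol is not consistent either. Sections 1.6 and 3.1 place the sample 28 (+14) days after each vaccination, Table 5 gives Day 57 -7/+14, and Section 3.5.7.2 collects unsolicited adverse events "from the time of the first dose administration at Day 1 through Day 57 (±7 days").

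**The concern.** There are two faults. The first is version drift: a SAP issued after protocol V3.0 still carries narrower windows, and its precedence clause would make them binding. The second is the anchor. The windows are fixed days from dose 1, but the visits after dose 2 follow the actual second dose, which may move by up to 14 days.

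PP is the primary immunogenicity population at every interim and at the final analysis, and Protocol 3.6.8 says the interims inform dose selection. If Appendix A governs PP membership, participants who kept to the current protocol drop out of the Day 29 or Day 57 GMT and seroconversion summaries. By-visit laboratory summaries in a first-in-human escalation study would lose or mislabel results from the week after dose 2, however the PP wording is read.

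**Working it through.** **1. Reproduce the SAP windows.** Day 29 +7 gives 29 to 36, and Day 57 ±7 gives 50 to 64. Both match Appendix A. The V3.0 allowances give 29 + 14 = 43 and 57 + 14 = 71, so [29,43] and [50,71].
- Day 29: Days 37 to 43 fall outside, 7 of 15 permitted days.
- Day 57 counted from dose 1: Days 65 to 71 fall outside, 7 of 22.

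**2. Which count applies.** Study day is date minus vaccination date plus 1. Counted from the most recent dose, the visits 7 and 28 days after dose 2 would be Days 8 and 29. Targets of 36 and 57 therefore fit only a count from dose 1.

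**3. Laboratory mapping.** Let D be the dose-2 day, 29 to 43 (Protocol 3.1). The 7-day laboratory visit has a +3 window (Protocol 3.5.8, Table 5), so its permitted days are D+7 to D+10. The relevant Appendix A windows are [29,36], [36,39] and [50,64].

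| D | 7-day labs, D+7 to D+10 | Labs taken before dose 2 on day D |
|---|---|---|
| 29 | All 4 days in Day 36 (Day 36 itself also in Day 29) | Day 29 |
| 30, 31, 32 | 3, 2, 1 of 4 days in Day 36; the rest in no visit | Day 29 |
| 33 to 36 | No visit | Day 29 (D = 36 also in Day 36) |
| 37 to 39 | No visit | Day 36, a post-dose visit |
| 40, 41, 42 | 1, 2, 3 of 4 days in Day 57; the rest in no visit | No visit |
| 43 | All 4 days (50 to 53) in Day 57 | No visit |

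For D = 33 to 39, which is 7 of the 15 permitted dose-2 days, no on-time 7-day sample maps to any visit. Days 33 to 36 lie inside even the SAP's own +7 dose window.

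**4. Day 57 counted from dose 2.** D + 28 ≤ 64 only if D ≤ 36, so for D = 37 to 43 a sample exactly 28 days after dose 2 is always outside. Under -7/+14 the permitted days are D+21 to D+42 (22 days), and the number inside is 64 - (D+21) + 1 = 44 - D, that is 7, 6, 5, 4, 3, 2, 1. Under 28 (+14) the permitted days are D+28 to D+42, and 0 of 15 are inside.

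**5. Precision if participants are lost.** The half-width of the log-scale GMT 95% CI is proportional to t(0.975, n-1)/√n when the SD is unchanged. The losses are assumptions for illustration; the starting sizes are the planned 24 per dose and 4 seropositive per dose.

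| n | Factor | Widening |
|---|---|---|
| 24 | 0.422 | reference |
| 22 | 0.443 | 5% |
| 18 | 0.497 | 18% |
| 12 | 0.635 | 50% |
| 4 (seropositive) | 1.591 | reference |
| 3 | 2.484 | 56% |

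**6. Whether the ITT check would show it.** SAP 6.2.1 uses ITT at the final analysis only. It repeats the primary immunogenicity analyses in ITT only if (ITT - overall PP)/PP exceeds 10%. SAP 6.2.2 puts anyone in any per-visit PP set, including Day 1, into the overall set. If all 120 stay in the Day 1 set, the difference is (120 - 120)/120 = 0%, however many Day 29 or Day 57 samples are excluded.

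**7. Later visits (secondary).** The month length is not stated; assume 28-day months counted from dose 2.
- Month 7, D+168 ±14 against [182,210]: 28, 21 and 14 of 29 days inside for D = 29, 36, 43.
- Month 13, D+336 ±14 against [343,385]: 29, 28 and 21 of 29.

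**The case against.** The best reply is that the printed days are nominal. Appendix A also gives fixed adverse-event frames such as [29,57], yet SAP 7.1 counts those periods from the actual doses. The Day 29 laboratory row names the date of the second vaccination as its target. SAP Appendix E sends the reader to protocol Table 5, which has the wider windows, and Protocol 3.6.5 uses the same phrase about acceptable windows. On that reading no compliant participant leaves the PP set. The study is also descriptive, all data are listed, and worst-grade laboratory shifts use scheduled and unscheduled results.

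Part of this stands. The PP loss is conditional on Appendix A governing, day counts are not participant counts, and the number affected could be zero. Counting -7/+14 from dose 2 stretches the visit to Day 85 (43 + 42), whereas Table 5 prints the allowance against nominal Day 57. The ±7 in Protocol 3.5.7.2 concerns adverse-event collection, not sampling.

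The rest does not rescue the table. It is titled as a set of mapping rules. The Day 29 row still carries the fixed window [29,36], and the Day 36 and Day 57 laboratory rows are plain fixed days. Only the adverse-event periods have separate text that ties them to the actual doses.

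**Conclusion.** The concern holds and should be fixed. The mismatch between the SAP and the current protocol is certain: 7 permitted days are cut at each of Day 29 and Day 57, with no declared reason. The laboratory mapping fails as written for a late second dose, assuming that the visits after dose 2 follow the actual dose, as Protocol 3.1 and 3.5.8 imply. The loss from the PP sets depends on Appendix A defining their windows, an ambiguity that itself needs closing. Its size in participants cannot be computed from the documents. The analyses exposed are the by-visit laboratory summaries and, conditionally, the Day 29 and Day 57 PP immunogenicity summaries. Primary adverse-event endpoints, worst-grade laboratory shifts and listings are not affected.

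**What to change.** - Rebase the SAP on protocol V3.0. Reconcile the +7 and +14 dose-2 windows, and the protocol's three Day 57 statements: 28 (+14), -7/+14 and ±7.
- In Appendix A, set the Day 29 window to the reconciled protocol window. Count Day 36 laboratory tests, Day 57, Month 7 and Month 13 from the actual dose-2 date, with a stated month length. Widening alone would not work, because [29,43] contains all of [36,39].
- State which study-day count each row uses, and make the laboratory windows non-overlapping.
- Have the PP definition in SAP 6.2.2 cite Appendix A.
- As a secondary improvement, apply the 10% ITT trigger to each per-visit PP set.

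The cost is a SAP amendment and reprogramming of the visit mapping. No new data or participants are needed.

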10.2 Appendix B Standards for Safety and Immunogenicity Variable Display in TFLs

Continuous Variables

The precision for continuous variables will be based on the precision of the data itself. The mean and median will be presented to one decimal place more than the original results; the SD will be presented to two decimal places more than the original results; the minimum and maximum will be presented to the same precision as the original results.

Categorical Variables: Percentages will be presented to 1 decimal place.

10.3 Appendix C Imputation Rules for Missing or Partial Medication Dates

Imputation rules for missing or partial medication start/stop dates are defined below:

- 1. Missing or partial medication start date:
 - a. If only DAY is missing, use the first Day of the month.
 - b. If DAY and Month are both missing, use the first Day of the year.
 - c. If DAY, Month and Year are all missing, the date will not be imputed, but the medication will be treated as though it began prior to the first vaccination for purposes of determining if status as prior or concomitant.
- 2. Missing or partial medication stop date:
 - a. If only DAY is missing, use the last Day of the month.
 - b. If DAY and Month are both missing, use the last Day of the year.
 - c. If DAY, Month and year are all missing, the date will not be imputed, but the medication will be flagged as a continuing medication.

Protocol mRNA-1893-P101 Date Issued: 25May2021

In summary, the prior, concomitant or post categorization of a medication is described below.

Table 4 Prior, Concomitant, and Post Categorization of a Medication

| | Stop Date | | |
|---------------------------------|-----------------------------|--------------------------|----------------------|
| _ | ≥ Date of First Vaccination | | |
| | < Date of First | and ≤ 28 days after Last | > 28 days after Last |
| Start Date | Vaccination | Vaccination | Vaccination [2] |
| < Date of First Vaccination [1] | P | PC | PCA |
| ≥ Date of First Vaccination | - | C | CA |
| and ≤ 28 days after Last | | | |
| Vaccination | | | |
| > 28 days after Last | - | - | A |
| Vaccination | | | |

A: Post; C: Concomitant; P: Prior

10.4 Appendix D: Imputation Rules for Missing AE dates

Imputation rules for missing or partial AE start/stop dates are defined below:

- 1. Missing or partial AE start date:
 - a. If only DAY is missing, use the first Day of the month, unless:
 - i. The AE end date is after the date of first vaccination or is missing AND the start Month and year of the AE coincide with the start Month and year of the first vaccination. In this case, use the date of first vaccination

^[1] includes medications with completely missing start date

^[2] includes medications with completely missing end date

Protocol mRNA-1893-P101

- b. If DAY and Month are both missing, use the first Day of the year, unless:
 - i. The AE end date is after the date of first vaccination or is missing AND the start year of the AE coincides with the start year of the first vaccination. In this case, use the date of first vaccination
- c. If DAY, Month and Year are all missing, the date will not be imputed. However, if the AE end date is prior to the date of first vaccination, then the AE will be considered a pre-treatment AE. Otherwise, the AE will be considered treatment-emergent.
- 2. Missing or partial AE end dates will not be imputed

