3 INVESTIGATIONAL PLAN

3.1 Study Design

This is a Phase 1, randomized, observer-blind, placebo-controlled, dose-ranging study to evaluate the safety, tolerability, and immunogenicity of Zika vaccine mRNA-1893 administered to healthy flavivirus-seropositive and seronegative adult participants (18 to 49 years of age, inclusive). A total of 120 participants (30 participants per cohort) will be enrolled into 1 of 4 mRNA-1893 dose cohorts (10, 30, 100, or 250 µg). Within each cohort, eligible participants will be randomly assigned to mRNA-1893 or placebo (4:1 mRNA-1893 to placebo) and administered the study vaccine as an IM injection on a 2-dose vaccination schedule, 28 days apart (Day 1 and Day 29). Participants will be stratified by baseline flavivirus serostatus (seropositive and seronegative).

The study will comprise a Screening Phase (up to 28 days), a Vaccination Phase (up to 57 days), and a Long-Term Follow-up Phase (up to 12 months after last vaccination) (Table 5). Participants will have approximately 8 clinic visits with an additional 13 safety telephone calls. Study duration will be approximately 13 months for each participant. Participants will provide written informed consent before any study-specific procedures are performed.

Study vaccine dosing will begin with Cohort 1 (10 µg mRNA-1893 or placebo), followed sequentially by Cohort 2 (30 µg mRNA-1893 or placebo), Cohort 3 (100 µg mRNA-1893 or placebo), and Cohort 4 (250 µg mRNA-1893 or placebo). Vaccine accountability, dose preparation, and vaccine administration will be performed by unblinded pharmacy personnel, who will not participate in any other aspects of the study. The remainder of the study staff and all participants will remain blinded to dosing assignment.

For each dose cohort (Cohort 1 through 4), Safety Oversight will be performed 7 days after the first 5 participants (all seronegative) are randomly assigned and receive the first study vaccination (Day 1). Once safety is confirmed, the remaining 25 participants in the dose level cohort will be randomly assigned to dosing. Seven days after all 30 participants in the cohort have received the first study vaccination, a blinded IST that is not directly involved in the day-to-day activities of the study, will review all available safety data for the currently dosed

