4.1 Primary Endpoints

The primary endpoints for the study are the following:

- Frequency and grade of each solicited local and systemic reactogenicity adverse reaction (AR) during a 7-day follow-up period after each vaccination
- Frequency and grade of any unsolicited adverse events (AEs) during the 28-day follow-up period after each vaccination
- Frequency of any medically attended adverse event (MAAE), serious adverse event (SAE), and adverse event of special interest (AESI) from Day 1 to the end of study (EOS) Visit at Month 13

Other safety assessments include clinical laboratory test results (hematology, serum chemistry, and coagulation); vital sign measurements; and physical examination findings.

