7.6.2 Adverse Events

An unsolicited AE is any AE reported by the participant that is either (1) not specified as a solicited AE in the protocol or (2) specified as a solicited AR in the protocol, but its onset occurs outside of the protocol-defined post vaccination period for reporting solicited AEs (ie, for the 7 days after each vaccination). A solicited ARs that meet the criteria for an SAE will also be recorded as an unsolicited AE.

A treatment-emergent AE (TEAE) is defined as any AE not present before exposure to vaccine or any AE already present that worsens in intensity or frequency after exposure. Only TEAEs are collected in this study.

An MAAE is defined as an AE that leads to an unscheduled visit to a healthcare practitioner.

Unsolicited AEs will be coded by PT and SOC using MedDRA and summarized by treatment, vaccination (first or second) and overall. Summaries for each vaccination will include AEs that occur during the 28 -day follow-up period after each vaccine.

All summaries of unsolicited AEs will present number and percentage of subjects in each category. For those summaries presented by PT, the preferred terms will be sorted in descending order of frequency within the mRNA-1893 treatment group.

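### SAP Appendix D guards partial AE start dates around dose 1 but not dose 2, so some post-dose-2 unsolicited AEs with no recorded day are dated before dose 2

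*SAP*

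**What the plan says.** SAP 10.4 (Appendix D), rule 1.a, covers an AE start date with a missing day: "If only DAY is missing, use the first Day of the month, unless" the AE ended after dose 1 (or has no end date) and "the start Month and year of the AE coincide with the start Month and year of the first vaccination". For that exception the instruction is: "In this case, use the date of first vaccination". Rule 1.b does the same by year when day and month are both missing. Neither rule mentions the second vaccination. End dates get no help: "Missing or partial AE end dates will not be imputed".

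One primary endpoint in SAP 4.1 is "Frequency and grade of any unsolicited adverse events (AEs) during the 28-day follow-up period after each vaccination". SAP 7.6.2 has unsolicited AEs "summarized by treatment, vaccination (first or second) and overall", each by-vaccination summary covering the 28 days after that dose. SAP 7.6.2.2 adds tables by vaccination, and by vaccination and grade. SAP 7.1 works out study day relative to the latest vaccination from dates.

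**The concern.** The exception stops an AE from being dated before exposure, which protects its treatment-emergent status. The trial has two doses and one primary endpoint is reported after each, so the same protection is needed at dose 2. Without it, a written rule puts some AEs under the wrong dose. The error has one direction: it lowers the frequency after dose 2 and can raise it after dose 1. Each dose level has 24 vaccine recipients (Protocol 3.6.4), so one participant moved changes a by-dose percentage by 1/24, about 4 percentage points.

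**Working it through.** The documents give no figure on this point, so there is none to reproduce.

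**Inputs from the documents**
- Imputation rules 1.a and 1.b: SAP 10.4.
- Dose 2 planned 28 days after dose 1, with a window of +14 days: Protocol 3.1. SAP 5.1 shows +7. Intervals of 28, 35 and 42 days were therefore tried.
- Follow-up of 28 days per dose: SAP 4.1 and 7.6.2.

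**Assumptions (not in the documents)**
- Dose 1 is equally likely on any calendar day; 1,461 consecutive dates (a four-year cycle) were enumerated.
- Onset after dose 2 is uniform unless stated otherwise.

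**Example.** Dose 1 is on 12 February 2020 and dose 2 on 11 March 2020. An AE begins on 16 March and is recorded only as March 2020. March is not the month of dose 1, so the AE is dated 1 March: 18 days after dose 1 and 10 days before dose 2. It is counted under dose 1.

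**Approximate share, dose 2 at +28 days.** An AE is misplaced if its onset is in dose 2's calendar month and dose 2 was not on the 1st. With an average month of 30.4 days:
- Onset on days 0 to 28 (mean 14): 1 − 14/30.4 − 1/30.4 = 1 − 0.461 − 0.033 = 50.7%.
- Onset on days 1 to 28 (mean 14.5): 1 − 14.5/30.4 − 1/30.4 = 49.0%.

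**Exact enumeration of rule 1.a, dose 2 at +28 days**

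| Onset after dose 2 | Dated before dose 2 |
|---|---|
| Uniform, days 0–28 | 21,492 / 42,369 = 50.7% |
| Uniform, days 1–28 | 20,079 / 40,908 = 49.1% |
| Early, days 0–7 only | 9,960 / 11,688 = 85.2% |
| Late, days 15–28 only | 5,337 / 20,454 = 26.1% |

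**Reverse direction.** For onsets between dose 1 and dose 2, 0 of 40,908 are dated on or after dose 2. The rule can only move such an AE to the 1st of its month or to the dose-1 date, and both precede dose 2.

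**Late dose 2 (onset days 0–28).** The share dated before dose 2 stays at 50.7%, but some imputed dates are then more than 28 days after dose 1:
- Dose 2 at +35 days: 7,730 / 42,369 = 18%.
- Dose 2 at +42 days: 14,597 / 42,369 = 34%.

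These AEs are in neither 28-day summary. For example, with dose 1 on 29 January 2020 and dose 2 on 11 March (+42 days), 1 March is 32 days after dose 1.

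**Rule 1.b.** With day and month both missing and dose 2 at +28 days, about 96% of post-dose-2 AEs are dated before dose 2, mostly because both doses fall in the same year.

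**Seven-day tables (SAP 7.6.2.3).** With uniform onset on days 1 to 28 and dose 2 at +28 days, the true share of day-missing post-dose-2 AEs within 7 days of dose 2 is 7/28 = 25%. The current rule places 29% within 7 days of one dose or the other. Adding a mirror-image exception that re-dates same-month AEs to the dose-2 date would place 73% there.

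**The case against.** The strongest objection is that the rule will rarely act. Unsolicited AEs are written daily on a diary card issued at each vaccination. Cards are reviewed at Days 8, 29, 36 and 57, and calls are made on Days 2, 3, 30 and 31 (Protocol 3.5.1, 3.5.2 and Table 5). Time of onset is a collected item (Protocol 3.5.7.3). Partial dates should therefore be few, though the documents give no number. This stands, and it limits the size of the point.

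The reach is also narrow. Overall counts and treatment-emergent status do not depend on which dose an AE follows. Tables pooling 28 days after any vaccination still capture a moved AE when dose 2 is on time; only the late-dose-2 loss reaches them. Solicited reactions are recorded on the diary by day.

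A further objection is that Protocol 3.5.7.3 lists dose among the AE items, which might settle attribution. But no SAP rule uses that item to place a partially dated AE, and SAP 7.6.2 defines the by-vaccination summaries by time after each dose.

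A reader might infer that half of all post-dose-2 AEs are misassigned, or that vaccine is biased against placebo. The documents support neither. The share applies only to AEs with no recorded start day and depends on the onset pattern. The rule is the same in every arm, the analysis is descriptive, and SAP section 8 says that differences from placebo will not be computed.

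**Conclusion.** The gap is real and minor. Appendix D misplaces a day-missing AE that began after dose 2 in dose 2's month, unless dose 2 was on the 1st, and makes no error in the other direction. Under uniform onset and a 28-day interval the share is 49% to 51%; it runs from 26% to 85% for late or early onset. These are shares of partially dated post-dose-2 AEs, whose number is unknown and should be small.

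A reader might also take every misplaced AE to be counted under dose 1. That is exact only when dose 2 is on time. At +35 or +42 days, 18% or 34% of all day-missing post-dose-2 AEs are lost from both by-dose summaries. The tables at risk are the by-vaccination unsolicited AE tables and, in part, the 7-day tables. The primary endpoint is touched only in its split by dose.

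**What to change.** In Appendix D, add an attribution rule for AEs with a partial start date whose month (rule 1.a) or year (rule 1.b) matches that of the second vaccination:

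- For the by-vaccination summaries, assign the AE to dose 1 or dose 2 from the diary card or Vaccination Phase contact (through Day 57) at which it was first recorded, or from a recorded before/after-dose-2 flag.
- Do not assign to dose 2 an AE that ended before dose 2.
- Do not re-date the AE to the dose-2 date. That would inflate the 7-day tables (73% against a true 25%, as shown above).
- Do not use reports first made in long-term follow-up for this assignment. Under rule 1.b they could otherwise be counted as early post-dose-2 events.

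The cost is a short SAP addition, plus carrying the reporting source or flag into the analysis data; the documents do not show that this is already done. A few AEs that began just before dose 2 but were first reported after it may be counted under dose 2. The 7-day and pooled 28-day tables would still use the imputed date, so their smaller error remains.
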